### **6.3 Medical history conditions and procedure history**

For rollover subjects, the medical history conditions and procedure history will be obtained directly from the Medical History CRFs and the Procedure History CRFs of the EP0083 and N01358 (for rollover subjects from N01379). If there is any new medical history condition, it will be collected in the Medical History Update form in EP0085. For direct enrollers, the medical history conditions and procedure history will be obtained from the Medical History CRFs and the Procedure History CRFs of EP0085. Reported medical history conditions are coded according with MedDRA version 18.1. Medical procedures are not coded. Start and stop date are documented partially with month and year only (yyyy-mm). No date imputation is foreseen.

#### **6.3.1 Previous and ongoing medical history conditions**

The number and percentage of subjects with a medical history condition, including both resolved and ongoing conditions, will be summarized by study group by the primary System Organ Class (SOC) and Preferred Term (PT).

A listing of subjects with previous and ongoing medical history conditions will be provided.

#### **6.3.2 Procedure history and concomitant procedures**

A listing of subjects with procedure history and concomitant procedures will be provided.

### **6.4 Prior and concomitant medications**

All prior and concomitant medications will be coded according to the WHODD version September 2017. Medications taken at study entry are the ongoing medications at the study entry of the core study. Previous medications are medications taken and discontinued prior to entry into the core study. Concomitant medications are medications taken during administration of BRV in EP0085 study. Previous AEDs and AED taken at core study entry will follow the AED definition according to the respective core study.

#### **6.4.1 Non-AEDs taken at study entry**

The number and percentage of subjects taking non-AEDs at study entry will be summarized for the Safety Set by primary therapeutic group (Anatomic Therapeutic Class [ATC] level 1), therapeutic subgroup (ATC level 2), and preferred drug name.

Non-AED taken at study entry refers to the core study entry. The non-AEDs at core study entry will follow the AED definition according to the respective core study. For rollover subjects the information will be obtained from CRF form “Prior and Concomitant Medications (including AEDs)” from EP0083 and CRF form “Prior and Concomitant Medications” from N01358 (for subjects from N01379). For direct enrollers the information will be obtained from EP0085 CRF form “Concomitant Medications (including AEDs)”.

#### **6.4.2 History of previous AED use**

The number and percentage of subjects who had taken at least 1 previous AED prior to entry into the core study will be summarized overall and by preferred drug name for the Safety Set. For rollover subjects the information will be obtained from CRF form “History of Previous Antiepileptic Drug Treatment” from EP0083 and N01358 (for subjects from N01379). For direct enrollers the information will be obtained from EP0085 CRF form “History of Previous Antiepileptic Drug Treatment”. Different with the core study N01358, for core study EP0083 (for the rollover subjects from EP0083) and EP0085 (for the direct enrollers), the history of previous AED was recorded in accordance with the list of AEDs as indicated in Appendix 3 of the study protocol, however, the Investigator’s judgement was prioritized and taken into consideration.

#### **6.4.3 Number of previous AEDs**

The number and percentage of previous AEDs will be summarized based on the following categorization: 0-1 AEDs, 2-4 AEDs, and  $\geq 5$  AEDs. The definition of previous AED use will be the same as section 6.4.2.

#### **6.4.4 AEDs taken at study entry**

The number and percentage of subjects taking AEDs at the core study entry visit will be summarized by preferred drug name for the Safety Set.

AED taken at study entry refers to the core study entry. The AEDs at core study entry will follow the AED definition according to the respective core study. Different with the core study N01358, for core study EP0083 (for the rollover subjects from EP0083) and EP0085 (for the direct enrollers), the AEDs taken at study entry was recorded in accordance with the list of AEDs as indicated in Appendix 3 of the study protocol and was captured according to the CRF “Core AED?” based on the Investigator’s judgement.

For rollover subjects the information will be obtained from CRF form “Prior and Concomitant Medications (including AEDs)” from EP0083 and CRF form “Prior and Concomitant Medications (AEDs only)” from N01358 (for subjects from N01379). For direct enrollers the information will be obtained from EP0085 CRF form “Concomitant Medications (including AEDs)”.

#### **6.4.5 Concomitant AEDs**

A concomitant AED is an AED which was taken during administration of BRV in EP0085 study, regardless of the start and stop date of the AED. Concomitant AEDs will be recorded in accordance with the list of AEDs as indicated in Appendix 3 of the study protocol and will be captured according to the CRF “Core AED?” based on the investigator’s judgement. The

number and percentage of subjects taking concomitant AEDs will be summarized by preferred drug name for the Safety Set.

#### **6.4.6        Vagus nerve stimulation (VNS)**

For all subjects, the VNS information will be obtained from EP0085 CRF form: Vagus Nerve Stimulation Status at Screening/Baseline. The number and percentage of subject who had VNS at Screening/Baseline of EP0085 will be summarized in a table. A listing of VNS status at study entry and VNS setting at the subsequent visits will be provided.

### **6.5            Potential drug-induced liver injury (PDILI) related information**

Subjects with potential drug-induced liver injury (PDILI) will be assessed to determine if IMP must be discontinued. If PDILI occurs, additional lifestyle and family medical history information will be collected. Listings of lifestyle and family medical history will be provided only if any subject reporting PDILI.

#### **6.6            Neuro-imaging procedure**

A neuro-imaging procedure, including brain magnetic resonance imaging (MRI), brain computerized tomography (CT) scan or other imaging test will be performed for direct enrollers at Screening Visit per Investigator discretion. A listing of CT and MRI data will be provided.

#### **6.7            Electroencephalogram**

For direct enrollers, if there is no appropriate EEG available within the last 10 years, a Baseline EEG must be scheduled at the SV and the results received before the EV. A listing of EEG interpretation data will be provided.

## **7                MEASUREMENTS OF TREATMENT COMPLIANCE**

Study drug compliance will not be calculated because the planned dose information is not collected and also due to the complexity associated with the interpretation of study drug compliance for this study. However, study drug compliance will be evaluated during the review of important protocol deviation. Study drug dosing will be provided in subject data listings.

## **8                EFFICACY ANALYSES**

All efficacy outcomes will be summarized with descriptive statistics only on the FAS. All efficacy analyses to the Evaluation Period will be based on the seizure records during the Evaluation Period on/after the first dose of BRV.

#### **8.1            Derivations of efficacy variable(s)**

The derivation and definition of efficacy variables in this study are addressed in this section.

##### **8.1.1        28-day adjusted seizure frequency**

The 28-Day Adjusted Partial Seizure Frequency (28DPSF) will be calculated by dividing the number of partial seizures by the number of days for which the DRC was completed and multiplying by 28, eg, as following equation:

$$28DPSF = \frac{\text{Number of partial seizures}}{\text{Number of days completed in the DRC}} \times 28$$

For the 28-day adjusted frequency of all seizure types (partial, generalized and unclassified epileptic seizure), the number of numerator will include partial, generalized and unclassified epileptic seizure.

### 8.1.2 Percent reduction of 28-day adjusted partial seizure frequency

Percent reduction of 28DPSF from Baseline is defined as the percentage reduction of 28DPSF for a designated post-baseline period in EP0085 compared with the Baseline 28DPSF in the core study. This variable will be derived as following equation:

$$\text{Percent reduction} = \frac{\text{Baseline 28DPSF} - \text{Post Baseline 28DPSF}}{\text{Baseline 28DPSF}} \times 100$$

For rollover subjects the Baseline seizure will be obtained from EP0083 and N01358 study. For direct enrollers, the Baseline seizure counts will be collected from 8 weeks prior to the first BRV administration (see section 3.3) and the number of days during the Baseline Period will be set as 56 days.

### 8.1.3 Responder rate of 28DPSF

A responder is defined as a subject with a  $\geq 50\%$  reduction of 28DPSF from the Baseline to the designated period.

### 8.1.4 Seizure freedom (partial, all epileptic seizure)

A subject is defined as seizure free for a designated period during the Evaluation Period if they meet **all of** the following criteria:

- Criteria 1: the subject completed the designated period during the Evaluation Period
- Criteria 2: the subject has at least 90% non-missing diary days during the period of time
- Criteria 3: the subject did not report any seizures during the period

## 8.2 Analysis of the efficacy variables

### 8.2.1 Analysis of seizure frequency per 28 day

Based on the definition in the Section 8.1.1, the partial seizure and all type seizures frequency per 28 days will be summarized by descriptive statistics for continuous parameters by study group. The analysis time intervals will be 3-month periods over the Evaluation Period. In addition, the partial seizure and all type seizures frequencies per 28 days all over the Evaluation Period will be summarized in the same way.

### 8.2.2 Analysis of percent reduction of 28DPSF

The percent reduction of 28DPSF from Baseline will be summarized by descriptive statistics as continuous parameters (refer to the Section 3.1) by study group. The analysis time intervals will be 3-month periods over the Evaluation Period. In addition, the percent reduction of 28DPSF all over the Evaluation Period will be summarized in the same way.

### **8.2.3 Analysis for responder rate of 28DPSF**

The number and percentage of responders will be summarized by study group. The analysis time intervals will be 3-month periods over the Evaluation Period. The denominator of percentage will be based on the total number of subjects with at least 1 seizure assessment during the time interval. The numerator will be the number of responders.

### **8.2.4 Analysis of seizure freedom**

Based on the definition of seizure free in the Section 8.1.4, the parameters in the following sub-sections will be analyzed respectively.

#### **8.2.4.1 The percentage of subjects continuously seizure-free**

The number and percentage of subjects who have been continuously seizure-free for partial seizure and all seizure types for at least 6 months and at least 12 months during the Evaluation Period will be summarized.

In addition to the 6 months and 12 months of intervals of continuously seizure-free, subsequent 6-month intervals will be summarized in a similar manner.

The percentage of subjects with continuously seizure-free will be based on the number of subjects exposed to BRV for at least the specific time interval.

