7.2 Treatments to be administered

Directly enrolled subjects in Japan and subjects rolling over from EP0083 will be started on a BRV dose of 100mg/day (2 equally divided doses administered twice daily) at study entry and should be maintained at this dose for at least 2 weeks, unless the subject is not able to tolerate treatment.

Subjects from Japan who entered from N01379 can enter EP0085 at a dose up to 200mg/day. The BRV dose can be adjusted based on the individual subject's seizure control and tolerability between 50mg/day and 200mg/day during the study and must always be administered in equal morning and evening doses except the last week of down-titration. Of note, decreasing the dose should not exceed 50mg/day.

For all subjects, the first intake of study medication should occur in the evening of the day of the EV. Subjects should take tablets according to instructions provided by the Investigator.

During the Down-Titration Period, the BRV dose may be decreased in steps of a maximum of 50mg/day on a weekly basis. A last down-titration step at 25mg/day for 1 week should be included prior to the 2-week Study Drug-Free Period. The subject will be required to enter a 2-week Study Drug-Free Period for 2 weeks, followed by a FV.

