12.3 Planned efficacy analyses

All efficacy outcomes will be summarized with descriptive statistics only on the FAS.

The 28-day adjusted seizure frequency will be calculated by dividing the number of partial seizures by the number of days for which the DRC was completed and multiplying by 28.

Planned efficacy analyses for rollover subjects in China and Japan include:

- Percent reduction in partial seizure frequency per 28 days from Baseline of EP0083 or N01358 to the Evaluation Period
- Responder rate in partial seizure frequency per 28 days over the Evaluation Period. A responder is defined as a subject with a $\geq 50\%$ reduction in seizure frequency from Baseline Period of EP0083 or N01358

Planned efficacy analyses for directly enrolled subjects in Japan include:

- Percent reduction in partial seizure frequency per 28 days from 8 weeks prior to BRV administration to the Evaluation Period
- Responder rate in partial seizure frequency per 28 days over the Evaluation Period. A responder is defined as a subject with a $\geq 50\%$ reduction in seizure frequency from 8 weeks prior to BRV administration

Planned efficacy analyses for all subjects (directly enrolled in Japan and rollovers in China and Japan) include:

- Seizure frequency per 28 days for partial seizures by 3-month periods over the Evaluation Period.
- Seizure frequency per 28 days for all seizure types (partial, generalized and unclassified epileptic seizure) by 3-month periods over the Evaluation Period.
- Percentages of subjects continuously seizure-free for partial seizure and all seizure types for at least 6 months and at least 12 months during the Evaluation Period.

- Seizure freedom (partial, all epileptic seizure) during the Evaluation Period.

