- Down-Titration Period (up to 4 weeks):

---

- If the subject is discontinuing study drug, the Investigator will first plan an EDV followed by the progressive down-titration of study drug.
- During the Down-Titration Period, the BRV dose may be decreased in steps of a maximum of 50mg/day on a weekly basis. A last down-titration step at 25mg/day for 1 week should be included prior to the 2-week Study Drug-Free Period.
- 2-week Study Drug-Free Period: After completion of the Down-Titration Period, or for those subjects who for extenuating circumstances do not complete a Down-Titration Period, the subject will be required to enter a 2-week Study Drug-Free Period, followed by a Final Visit (FV).

Subjects who will be converted to the commercial BRV product will complete an End of Study Visit without entering the Down-Titration Period or the 2-week Study Drug-Free Period and will not complete an FV.

Visits should occur on the specified Visit/Week. A  $\pm 7$  day window for each specified Visit/Week is allowed, provided the subject has adequate investigational medicinal product (IMP) to sustain the visit window. The end of the study is defined as the date of the last visit of the last subject in the study.

EP0085 will continue until the market approval of BRV, or until the sponsor decides to close the study, whichever comes first. In the event that market approval is not requested or obtained in the participant country, the subject will be able to continue in EP0085 for two years after entering EP0085.

In Japan, EP0085 will continue as a postmarketing clinical study (Phase 4) after the date of approval of BRV for the partial seizure indication.

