### 3.2 Analysis time points

#### 3.2.1 First and last dose of BRV

Unless otherwise noted, all references to the first dose of BRV in this SAP refer to the first dose of BRV during EP0085 (ie, not the first dose of BRV from the previous study in which subjects participated in prior to EP0085). Unless otherwise noted, all references to the last

known dose of BRV in this SAP refer to the last dose of BRV taken across any study periods (ie, the last dose of BRV across both the Evaluation and Down-Titration Periods).

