### 3.2.5 Study periods

The following study periods are defined for the classification in summary that are based on the study design:

Baseline Period	For rollover subjects from EP0083, the Baseline Period corresponds to the Baseline Period of EP0083 and is defined as study days on or after EP0083 Visit 1 date and prior to EP0083 Visit 3 date.  For rollover subjects from N01379, the Baseline Period corresponds to the Baseline Period of N01379 and is defined as study days on or after N01358 Visit 1 date and prior to N01358 Visit 3 date.  For direct enrollers, except for seizure outcome the Baseline Period is defined as study days on or after EP0085 Visit 0 date and prior to EP0085 Visit 1 date. The Baseline Period for seizure outcome is defined as 8 weeks prior to the first BRV administration (see section 8.1.2).
Evaluation Period	The Evaluation Period starts on the date of Visit 1 and the following algorithm is used to determine the end date:  If the subjects enter the Down-Titration Period: 

- for completed subjects, which is indicated by the CRF “Study Termination” form (Complete subject), the Evaluation Period ends on the date of End of Study Visit date.

- for discontinued subjects, which is indicated by the CRF “Study Termination” form (Dropout), the Evaluation Period ends on the date of EDV date.

 If the subjects do not enter the Down-Titration Period:  For complete / discontinued subjects who do not enter the Down-Titration Period, the end of Evaluation Period will be the date of last dose of BRV.
Down-Titration Period (up to 4 weeks)	If the subject is discontinuing BRV, the Investigator will first plan an EDV followed by the progressive down-titration of study drug.

A subject is considered entering Down-Titration Period only if the subject has an EDV and has at least 1 dose of study drug after the date of EDV, the start date of Down-Titration Period is set as 1 day after the date of EDV, and the Down-Titration Period ends on date of last dose of BRV. A subject without an EDV but having a termination CRF or with an EDV but without any dosing of study drug after the EDV will not have the Down-Titration Period, and no artificial Down-Titration Period will be created for analysis.

Study Drug-Free Period (2 weeks)

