### **9.1 Extent of exposure**

#### **9.1.1 Study medication duration and total study medication duration in subject-years**

Duration of exposure to study medication is defined as the total number of days a subject is exposed to study medication and will be calculated as the date of last dose in EP0085 minus date of first dose in EP0085 plus one in days. If the last dose date on the Study Termination / Early Discontinuation page is missing the last dose date will be captured from the Drug Dosing Log CRF. Gaps in BRV treatment or days on the Drug Dosing Log CRF with unknown dosing and/or partial missing exposure date will not be subtracted from the total duration of exposure.

Total study medication duration in subject-years will be calculated as the total duration of exposure in days divided by 365.25.

The duration of exposure to study medication will be summarized by study group for all subjects in the SS and will be presented in a table by summary statistics.

The subject cumulative exposure duration will then be classified into one of the following categories:  $>0$  month,  $\geq 3$  months,  $\geq 6$  months,  $\geq 12$  month,  $\geq 18$  month,  $\geq 24$  months,  $\geq 36$  months,  $\geq 48$  months, and so forth in 12-month increments up to the maximum duration of

exposure and will be presented as the number and percentage of subjects in each duration category by BRV overall and by modal dose group. Percentages for BRV overall will be computed based on the Safety Set. Percentages for the modal dose group will be computed based on the number of subjects exposed overall or within each duration of exposure.

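### SAP 8.2.3 plans no responder rate over the whole Evaluation Period, and the SAP 8.2.4.1 denominator counts down-titration days that its numerator cannot use (minor)

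*SAP*

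**What the plan says.** **Responder rate.** Protocol 12.3 lists "Responder rate in partial seizure frequency per 28 days over the Evaluation Period", and SAP 2.2.2 carries the same variable. In the same protocol section, seizure frequency is explicitly planned by 3-month periods; the responder rate is not. Protocol 12.6 also promises results overall. SAP 8.2.3 plans responders by 3-month interval only. The neighbouring sections differ: SAP 8.2.1 (seizure frequency) and 8.2.2 (percent reduction) each add a summary over the whole Evaluation Period, and 8.2.4.2 (seizure freedom) is a whole-period result. SAP 3.8 records no departure from the protocol.

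**Continuous seizure freedom.** SAP 8.2.4.1 makes the percentage "based on the number of subjects exposed to BRV for at least the specific time interval". The numerator follows SAP 8.1.4, where the first requirement reads "Criteria 1: the subject completed the designated period during the Evaluation Period". Exposure is "calculated as the date of last dose in EP0085 minus date of first dose in EP0085 plus one in days" (SAP 9.1.1), and unless otherwise noted the last dose means "the last dose of BRV across both the Evaluation and Down-Titration Periods" (SAP 3.2.1). For a discontinued subject who tapers, SAP 3.2.5 ends the Evaluation Period at the Early Discontinuation Visit (EDV), and "the start date of Down-Titration Period is set as 1 day after the date of EDV".

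**The concern.** Maintenance of efficacy over time is the secondary objective, and these are two of its main summaries.

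For the responder rate, a result that both documents define has no planned table. A reader of the report would find whole-period results for frequency, percent reduction and seizure freedom, but not for response. A subject who leaves in the first three months would appear in no responder table.

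For continuous seizure freedom, numerator and denominator use different clocks. Take two discontinued subjects with the same Evaluation Period of just under 180 days. One takes no dose after the EDV and is left out of the 6-month percentage. The other tapers past Day 180 and is counted as not seizure-free, whatever the diary shows. The difference comes from the taper, not from seizures.

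**Working it through.** The plan states no figure to reproduce: there is no sample size calculation and no hypothesis test. The check is date arithmetic and a small example.

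**1. Can the interval tables supply the whole-period responder rate?** Assume a baseline of 8 partial seizures per 28 days and four intervals with equal diary days.

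- Frequencies 3, 3, 3, 8: reductions 62.5, 62.5, 62.5, 0%. The mean is 17/4 = 4.25 and the whole-period reduction (8 - 4.25)/8 = 46.9%. This subject responds in 3 of 4 intervals but is a non-responder overall.
- Frequencies 3, 4.5, 3, 4.5: reductions 62.5, 43.75, 62.5, 43.75%. The mean is 15/4 = 3.75 and the reduction (8 - 3.75)/8 = 53.1%. This subject responds in 2 of 4 intervals but is a responder overall.

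The interval tables therefore do not fix the whole-period result in either direction.

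**2. Who is in no responder table?** SAP 3.2.6 admits a subject to a 3-month efficacy interval only if the last Evaluation Period dose is on or after the interval's last day, which is Day 90 for the first. Per Protocol 7.2, "the first intake of study medication should occur in the evening of the day of the EV", so the Entry Visit is Day 1 and a visit at week w falls on Day 7w + 1. A subject who stops at the scheduled Month 3 visit (Week 12) does so on Day 85 and enters no interval. The documents give no rate of stopping this early. For scale only, an assumed 2%, 5% or 10% of the 217 planned subjects is 4, 11 or 22; the FAS may be smaller.

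**3. Continuous seizure freedom: the mismatch window.** Let E be the days from first dose to the EDV, D the taper days and T the threshold (30-day months: 180 or 360).

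- Denominator: exposure E + D is at least T.
- Numerator: requires E to be at least T.
- In the denominator but unable to enter the numerator: T - D ≤ E ≤ T - 1.

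SAP 2.3 says "the BRV dose may be decreased in steps of a maximum of 50mg/day on a weekly basis", with a last week at 25mg/day and up to 4 weeks in all. The shortest permitted sequences are therefore 7, 14, 21 or 28 days from 50, 100, 150 or 200mg/day. Smaller steps are allowed, so for the lower doses these are minimum lengths; 28 days is the limit for all.

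- D = 28: Day 152-179 for 6 months, Day 332-359 for 12 months.
- D = 7: Day 173-179 and Day 353-359.

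Scheduled visits fall inside the 28-day windows. An EDV at Week 24 is Day 7 x 24 + 1 = 169; with 14 taper days, exposure is 183 against an Evaluation Period of 169. An EDV at Week 48 is Day 337; 28 taper days give 365.

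**4. Size.** Assume dropout d per 90 days, constant over time, with every leaver tapering for D days. The share of the denominator that cannot reach the numerator is 1 - (1 - d)^(D/90), and the loss in points is the true percentage times that share.

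| Taper | d = 2% | d = 5% | d = 10% |
|---|---|---|---|
| 7 days | 0.16% | 0.40% | 0.82% |
| 14 days | 0.31% | 0.80% | 1.63% |
| 28 days | 0.63% | 1.58% | 3.22% |

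A true 20% becomes 19.94% to 19.67% with 14 days. Over assumed true rates of 10% to 30%, the loss runs from 10 x 0.0016 = 0.02 points (7 days, d = 2%) to 30 x 0.0322 = 0.97 points (28 days, d = 10%).

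**5. After the change.** If the denominator also requires E to be at least T, the window is empty.

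**The case against.** **On the responder rate.** The amendment history in SAP 13.2 shows that the 8.2.3 wording was edited, so the omission may be deliberate. Each subject's whole-period percent reduction is already derived for 8.2.2, and response is a 50% cut of that value; listings will show key derived variables. This stands as far as it goes: the data exist and nothing is lost. It does not supply the table. SAP 3.1 limits the 8.2.2 summary to n, mean, SD, median, minimum and maximum, from which the proportion at or above 50% cannot be read. If the omission is deliberate, SAP 3.8 should say so.

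**On continuous seizure freedom.** SAP 8.2.4.1 neither defines exposure nor cites 9.1.1, which is a safety section, and 3.2.6 shows the authors using Evaluation Period dosing for efficacy. They may have meant that here. However, 3.2.1 makes the whole-study last dose the default unless noted, 8.2.4.1 notes nothing, and 3.2.6 exempts continuous seizure freedom from its 3-month intervals. It is also fair that counting someone who left before Day 180 as not having achieved six months is conservative, and that the 90% diary rule in 8.1.4 already keeps some subjects in the denominator with no route to the numerator. This limits the weight of the point. It does not explain why a taper should decide who is counted.

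**Stronger readings that the documents do not support.** A reader might infer that 8.2.3 and 3.2.6 set conflicting responder denominators. They need not: 3.2.6 covers 3-month efficacy analyses generally, except continuous seizure freedom, and the requirement in 8.2.3 for one seizure assessment fits inside it. Sections 8.2.1 and 8.2.2 do not repeat the rule either. A reader might also infer that the interval percentages drift upward as non-responders leave. That needs differential dropout, for which the documents give no figure, and attrition is reported under SAP 5.1 and 5.4.

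**Conclusion.** Both points hold and both are minor.

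The firmer one is the responder rate. A variable defined over the Evaluation Period in the protocol and in SAP 2.2.2 has no whole-period analysis in SAP 8.2.3, no change is declared, and the planned interval tables cannot stand in for it. This rests on the text alone.

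The denominator mismatch follows from the SAP's default definitions of last dose and exposure. It affects only discontinued subjects who taper and whose Evaluation Period ends within 28 days before a threshold. It lowers the percentage slightly. The figure of less than about 1 point rests on assumed dropout of 2-10% per 90 days, assumed true rates of 10-30%, and every leaver tapering. Those who take no dose after the EDV do not contribute, so the 28-day row overstates the effect for a given dropout rate. The rows for shorter tapers are not upper limits, because slower tapers are allowed.

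Neither point affects the primary safety objective. It would be wrong to infer that the seizure-freedom results are materially distorted.

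**What to change.** - **SAP 8.2.3:** add the number and percentage of responders over the whole Evaluation Period, by study group on the FAS, worded like the last sentence of 8.2.2. SAP 3.8 then needs no entry for it.
- **SAP 8.2.4.1:** base the denominator on FAS subjects whose time from first dose to the end of the Evaluation Period, as defined in 3.2.5, is at least the interval, in place of total BRV exposure.

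The cost is two SAP sentences and one extra column in the responder table, with no new data. The drawback is that a whole-period responder rate mixes short and long follow-up, as the whole-period percent reduction in 8.2.2 already does. The revised seizure-free denominator is slightly smaller and remains conditional on staying in the Evaluation Period for the interval.
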